4.1 Inclusion Criteria

1. Age \geq 18 and $<$ 90 years.
2. Willing to participate in the study and competent to provide informed consent.
3. Willing to comply with protocol procedures.
4. Has an underlying diagnosis of osteoarthritis indicated for a total knee arthroplasty.

4.2 Exclusion Criteria

1. The patient must not have taken a schedule II narcotic daily, for 7 consecutive days, during the 3 months leading up to the surgery
2. The patient must not be allergic or intolerant to a medication used in the multimodal pain pathway
3. Revision knee arthroplasty
4. Uncontrolled diabetes with A1C $>$ 8.0 %
5. Pregnant patients

4.3 Subject Recruitment, Enrollment and Screening

Subjects will be identified and enrolled from the principal investigator and co-investigator's clinical practices. If the patients are eligible for the study and wish to participate then they will be enrolled.

4.4 Early Withdrawal of Subjects

4.4.1 When and How to Withdraw Subjects

Subjects will be withdrawn from the study prior to completion if they ask to be removed from the study. They will also be withdrawn if they do not complete the protocol requirements or have a serious adverse reaction to one of the medications in the multi-modal regimen. Finally, subjects may be withdrawn from the study at the discretion of the treating physician.

4.4.2 Data Collection and Follow-up for Withdrawn Subjects

If subjects are withdrawn from the study prior to completion we will collect the data prior to withdrawal. At the conclusion of the study we will note the number of subjects that were withdrawn from the study as well as the reasons for withdrawal.

5 Study Drug

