surgery and bolused with 10 mL of 0.5% ropivacaine. The pumps will be loaded with saline (single shot adductor canal group), or ropivacaine 0.2%, dispersed in either a continuous infusion (6 mL/hr) or pulsed intermittent bolus (8 mL every 2 hours). All groups will have a patient demand dose of 6 mL/hr for anterior knee pain. The medication for the adductor catheter will be dispersed to the anesthesia team by the research pharmacy. The anesthesia team will place the catheter under ultrasound guidance in the recovery room. They will adjust the delivery mode based on patient randomization. The anesthesia team will record the serial number of the pump at the time of placement.

Questionnaires will be sent electronically to the patient. Results will be collected daily for 14 days postoperatively, followed by weekly questionnaires until they discontinue narcotic medications. Additional questionnaires will be collected at 30 and 60 days postoperatively in order to record pain and KOOS Jr. scores. The questionnaires will be sent in the morning; if a patient fails to fill out the questionnaire by the afternoon, a member of the research team will contact the patient to obtain the data. The questionnaires will document numerical rating scale (NRS) pain scores, information on symptoms of nausea, vomiting, and constipation, and will inquire if the patient is still consuming narcotic medication.

Following discontinuation of the catheter the patient will remove and return the device to the supplier. The supplier will then provide the rate of on-demand usage to the research team by way of device serial number. This information will be stored in Redcap.

Subjects will be withdrawn prior to completion if they ask to be removed from the study. They may also be withdrawn from the study if they have a serious adverse reaction to one of the prescribed medications. Finally, subjects may be withdrawn at the discretion of the treating physician. If subjects are withdrawn early their last recorded pain score will be carried forward until study conclusion in order to perform intention to treat analysis. The study will continue to ascertain duration of narcotic use with weekly questionnaires, until the patient has stopped the medication.

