3.5 Secondary Study Endpoints

The secondary endpoints will be the amount of medication administered via the patient-controlled function on the adductor catheter as well as duration of narcotic use required in each cohort. We hypothesize that the intermittent bolus cohort will require fewer doses of patient-administered medication and will use narcotic medication for a shorter duration when compared to the continuous infusion and placebo groups.

We will additionally calculate the overall morphine equivalents used in each cohort during their hospitalization, and dividing this by the total number of post-surgical hospitalization hours in order to normalize the data.

Nausea and vomiting will be recorded daily using the postoperative nausea and vomiting scale and compared between groups. Presence of constipation will be a subjective rating by the patient that is also recorded daily. We will compare the post-surgery length of hospitalization between groups. Finally, we will compare patient-reported outcomes using the KOOS Jr. questionnaire.

We hypothesize that the intermittent bolus cohort will use less narcotic mediation and will therefore have lower rates of constipation, nausea and vomiting. Furthermore, we believe this cohort will demonstrate equivalent lengths of stay and patient-reported outcomes as compared to the comparison groups.

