3.6 Primary Safety Endpoints

If patients report serious adverse side effects from a medication in the multi-modal regimen, or if they report uncontrolled pain, they will be withdrawn from the study and provided alternative medication per the treating surgeon's discretion.

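### In-hospital opioid use and length of stay have no stated collection to discharge once a patient is withdrawn, although uncontrolled pain is itself a reason for withdrawal

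*Combined protocol and SAP*

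**What the plan says.** **Endpoints.** Section 3.5 lists among the secondary endpoints "We will additionally calculate the overall morphine equivalents used in each cohort during their hospitalization", divided by post-surgical hospital hours, and also "We will compare the post-surgery length of hospitalization between groups". Both need data up to discharge.

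**Withdrawal triggers.** Under 3.6, if patients have serious side effects "or if they report uncontrolled pain, they will be withdrawn from the study and provided alternative medication per the treating surgeon's discretion". Section 8.5 also withdraws patients whose pain becomes intolerable without more narcotic.

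**Data after withdrawal.** Section 4.4.2 states "If subjects are withdrawn from the study prior to completion we will collect the data prior to withdrawal" and provides for nothing later except counting withdrawals and their reasons. Section 3 (Study Design) makes two exceptions: "If subjects are withdrawn early their last recorded pain score will be carried forward until study conclusion in order to perform intention to treat analysis", and "The study will continue to ascertain duration of narcotic use with weekly questionnaires, until the patient has stopped the medication".

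**Analysis.** Section 7.2 commits to intention to treat and leaves the missing-data method open: carry-forward, regression or something else, according to how much is missing. Section 7.3 puts in the final analysis those patients who completed the study.

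**The concern.** A patient withdrawn before discharge for uncontrolled pain is one whose opioid need has just risen. Under 4.4.2 the opioid given after that moment, and the discharge time, are not collected. The section 3 exceptions do not help, because a pain score and a stop date for narcotics give neither an in-hospital amount nor a length of stay. The loss is therefore tied to the outcome being compared, and it may differ by arm if one arm has weaker analgesia.

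Section 7.1 says this study will supply the data for powering a larger one. A distorted opioid difference would carry forward into that calculation. The hospital should already hold both items for every operated patient, so the loss is avoidable.

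**Working it through.** **1. The plan's own figures.** The significance threshold is 0.05/3 = 0.0167 and the total is 3 × 28 = 84; both reproduce. Section 7.1 says there was no formal power analysis, so there is none to check. The only withdrawal figure is the interim rule in 7.2 (50% of the first 20, that is 10 patients). It is a stopping threshold, not an expected rate, and it is not confined to withdrawals in hospital.

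**2. What the plan yields for a patient withdrawn in hospital.**
- Opioid rate: the patient may be dropped (7.3), imputed by a method chosen later (7.2), or given a rate from pre-withdrawal data. Dividing that opioid by full hospital hours needs the discharge time, which 4.4.2 does not collect. Dividing by pre-withdrawal hours is possible but nowhere stated.
- Length of stay: time to withdrawal is not time to discharge, so there is no value unless one is imputed.
- Carry-forward has no natural meaning for a single total or a discharge time.

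**3. Direction of the bias.** All inputs here are assumptions. Let *w* be the share withdrawn in hospital, *c* the mean rate in completers, *h* the full-stay rate of withdrawn patients, and *r* the recorded pre-withdrawal rate divided by the full-stay rate.

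Arm mean = (1 − w)·c + w·h·r, with r = 1 for full-stay data. The completers-only mean is c.

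Take c = 1.5 (saline) and 1.0 (bolus) morphine equivalents per hour, and h = 3.0. With 20% vs 5% withdrawn:
- Full stay: (0.8 × 1.5 + 0.2 × 3.0) − (0.95 × 1.0 + 0.05 × 3.0) = 1.80 − 1.10 = 0.70
- Completers only: 1.5 − 1.0 = 0.50
- r = 0.5: (1.20 + 0.30) − (0.95 + 0.075) = 0.475
- r = 1.3: (1.20 + 0.78) − (0.95 + 0.195) = 0.835

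| Withdrawn, saline vs bolus | Full stay | Completers only | r = 0.5 | r = 1 | r = 1.3 |
|---|---|---|---|---|---|
| 20% vs 5% | 0.70 | 0.50 | 0.475 | 0.70 | 0.835 |
| 10% vs 10% | 0.45 | 0.50 | 0.45 | 0.45 | 0.45 |
| 5% vs 20% | 0.175 | 0.50 | 0.40 | 0.175 | 0.04 |

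The difference shrinks in the first row when patients are dropped or r is below 1. It is unchanged or larger in several other cells. If opioid is divided by full hours, r cannot exceed 1. If it is divided by pre-withdrawal hours, r can lie on either side of 1.

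**4. Effect on the test.** Simulation with assumed inputs: 28 per arm, lognormal rate with log SD 0.6, patients above a common rate of 2.5 withdrawn, Wilcoxon test at 0.0167, 2,000 runs per setting. Each cell shows mean difference; power.

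| Log shift (withdrawn) | Full stay | Completers only | r = 0.5 | r = 1.3 |
|---|---|---|---|---|
| 0.5 (about 24% vs 6%) | 0.78; 0.71 | 0.35; 0.41 | 0.42; 0.62 | 0.98; 0.71 |
| 0.3 (about 15% vs 6%) | 0.42; 0.27 | 0.22; 0.17 | 0.26; 0.24 | 0.52; 0.28 |

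At r = 1.3 power stays at its full-stay value because the withdrawn patients already hold the top ranks. No corresponding calculation was made for length of stay.

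**The case against.** The strongest reply is that this is an unspecified rule rather than a lost endpoint. A reader might infer that withdrawn patients cannot be scored at all. The documents do not support that: 7.2 allows regression or another imputation under intention to treat, and 9.2 names hospital records among its examples of source documents. A reader might also infer that all collection stops at withdrawal. Section 3 continues the follow-up of narcotic duration, so that is too broad.

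It can also be said that few withdrawals may happen before discharge. Section 3.1 already includes as-needed oxycodone and IV narcotic, and 1.5 describes the latter as a safety net for uncontrolled pain. Opioid given under that regimen before any withdrawal is counted. Further, these endpoints are not among the stated aims, and the study is a pilot without a power target, so a fall in power is not a shortfall against anything the plan promised.

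All of this stands as a limit on size and wording. It does not supply a collection rule. Naming hospital records as source documents does not say they are abstracted after withdrawal, regression would estimate values the hospital should already hold, and 7.3 taken literally overrides the intention-to-treat statement for exactly these patients.

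**Conclusion.** The concern holds in this form: for patients withdrawn before discharge, the plan does not provide for collecting opioid use and discharge time after withdrawal, the reason for withdrawal is close to the opioid outcome, and 7.2 and 7.3 disagree on whether such patients are analysed.

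It is tempting to conclude that the opioid difference between arms must shrink. The documents do not show that. Shrinkage is the likely direction if in-hospital pain withdrawals concentrate in the higher-use arm and those patients are dropped or their later, higher use is cut off. With balanced withdrawal, more withdrawal in the lower-use arm, or a pre-withdrawal rate at or above the full-stay rate, the bias can be nil or reversed. For length of stay neither direction nor size can be stated.

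Every magnitude above rests on assumed rates, spread and withdrawal shares, and the simulation further assumes that the highest users are the ones withdrawn. The figures show what could happen, not what to expect. Since these are secondary endpoints in a pilot, this is a worthwhile and cheap correction rather than an essential one. Full collection removes this source of bias, whichever way it runs, wherever authorization allows.

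**What to change.** - **4.4.2:** add, for example: *For every randomised patient who had surgery and has not revoked authorization, in-hospital opioid administrations and discharge date and time will be taken from the medical record through discharge, whether or not the patient is withdrawn.*
- **3.5 and 7.2:** analyse both endpoints on these full values for all randomised patients who had surgery, counting opioid given after withdrawal and all post-surgical hospital hours.
- **7.3:** amend so that these patients are not excluded as non-completers, and reconcile it with section 3, 4.4.2 and 7.2.

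The cost is a few sentences and a little extra chart abstraction. Consent and authorization wording must cover use of the record after withdrawal. Patients who revoke authorization (9.1) before discharge would still have missing values. No treatment or withdrawal rule is changed.

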5.1 Description

See section 3.1 for the multi-modal pain regimen that will be used.

5.2 Treatment Regimen

See section 3.1 for the multi-modal pain regimen that will be used.

5.3 Method for Assigning Subjects to Treatment Groups

Patients will undergo computer randomization by the research pharmacy prior to dispensing the medication in order to ensure that the treating physician (surgeon) remains blinded to the study.

5.4 Preparation and Administration of Study Drug

The medication that will be loaded in the adductor catheter will be dispensed by the research pharmacy to the anesthesia team to ensure blinding of the surgical team.

5.5 Subject Compliance Monitoring

Patient compliance during the hospitalization will be tracked by the surgical team. Following discharge patients will be contacted daily for 2 weeks, followed by weekly questionnaires until they have discontinued all narcotic medication.

5.6 Prior and Concomitant Therapy

If a patient has taken a narcotic medication (schedule II) in the 3 months leading up to surgery they will be excluded from the study. Patients may request and be provided refills for narcotic medication at the discretion of the treating surgeon.

5.7 Packaging

The medication will be provided by the research pharmacy and dispensed to the anesthesia team for loading into the adductor canal pain catheter. This will be secured until the medication is fully dispensed.

5.8 Masking/Blinding of Study

This will be a double-blinded study. Computer randomization will be used for patient grouping and the research pharmacy will dispense the medication to the anesthesia team, who will set the adductor catheter dosing based upon randomization. The surgical team and patient will remain blinded to the medication and dosing regimen.

5.9 Receiving, Storage, Dispensing and Return

5.9.1 Receipt of Drug Supplies

Not applicable

5.9.2 Storage

Once dispensed to the anesthesia team, the medication will be loaded into the adductor canal catheter, which will be secured until the medication is fully dispensed.

5.9.3 Dispensing of Study Drug

The adductor catheter settings (continuous versus intermittent bolus infusions) will be selected by the anesthesia team, based upon patient randomization. This information will be provided to the anesthesia team by the research pharmacy in order to maintain blinding of the surgical team.

5.9.4 Return or Destruction of Study Drug

After the medication has been fully dispensed (postoperative day #4), patients will remove the adductor catheter and send the pump to Avanos for processing.

6 Study Procedures

6.1 Visit 1

At visit #1 patients will be screened for eligibility for inclusion in the study. If agreeable, an informed consent will be signed.

6.2 Visit 2

[figure not shown]
Patients will undergo standard preoperative clearance testing.

6.3 Visit 3

Patients will then proceed with the total knee replacement procedure. During the hospitalization we will record daily pain, nausea, vomiting, and constipation levels. Following the hospitalization these values will continue to be recorded daily utilizing an online questionnaire. If patients fail to complete the questionnaire then we will contact the patient via phone to record the daily value.

6.4 Visit 4

At 2 weeks the patients will return for a standard postoperative visit. The patient will then receive an online questionnaire weekly until they discontinue narcotic medication. They will receive additional surveys at 30 and 60 days following surgery.

7 Statistical Plan

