Study Product, Dose, Route, Regimen	This study will evaluate the efficacy of adductor canal pain catheters following total knee arthroplasty, using either an intermittent bolus or continuous infusion compared to a single-shot adductor canal block.
Duration of Administration	4 days
Reference therapy	Single-shot adductor canal block
Statistical Methodology	Statistical analysis will be performed on the basis of the intention to treat principle. Comparisons between treatment groups will be made using Wilcoxon rank sum test or Fisher's exact test.

1 Introduction

This document is a protocol for a human research study. This study will be carried out in accordance with the applicable United States government regulations and Mayo Clinic research policies and procedures.

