7.2 Statistical Methods

Descriptive and Inferential Statistics

Continuous variables will be summarized with the sample mean, median, standard deviation, minimum, 25th percentile, 75th percentile, and maximum. Categorical variables will be summarized with number and percentage of patients. All analysis will be performed on the basis of the intention-to-treat principle. Comparisons of endpoints between the three treatment arms will be made using a Wilcoxon rank sum test (continuous or ordinal endpoints) or Fisher's exact test (categorical endpoints). Missing data will be imputed using either the last observation carried forward method, a regression-based approach, or another method, depending on the extent of missing data. In order to adjust for the three pair-wise comparisons between treatment groups that will be made for each endpoint, we will utilize a Bonferroni correction for multiple testing, after which p-values of < 0.0167 will be considered as statistically significant. All statistical tests will be two-sided.

Primary Hypothesis:

We hypothesize that the intermittent bolus infusion cohort will report improved pain scores compared to continuous infusion catheters and placebo cohorts.

Secondary Hypothesis:

We hypothesize that the intermittent bolus cohort will require fewer doses of patient-administered medication and will use narcotic medication for a shorter duration when compared to the continuous infusion and placebo groups.

Interim Analysis

We will evaluate the first twenty patients. If 50% of the patients are withdrawn from the study for poor pain control or serious adverse reactions to the study medication, then we will close the study early.

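### The end of the infusion is tied to two events that cannot coincide for all patients, so Aim 2's demand amount may not be comparable between arms unless it is divided by pump time

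*Combined protocol and SAP*

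**What the plan says.** The Study Summary gives "Duration of Administration 4 days". Section 5.9.4 (Return or Destruction of Study Drug) says "After the medication has been fully dispensed (postoperative day #4), patients will remove the adductor catheter", which makes an empty pump and day 4 the same moment. Section 5.9.2 (Storage) again refers to the pump running out: "the medication will be loaded into the adductor canal catheter, which will be secured until the medication is fully dispensed". Section 5.7 (Packaging) is worded similarly.

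Section 3 (Study Design) gives the pump settings. The active pumps are "dispersed in either a continuous infusion (6 mL/hr) or pulsed intermittent bolus (8 mL every 2 hours"), and "All groups will have a patient demand dose of 6 mL/hr for anterior knee pain". For the third arm it says only "The pumps will be loaded with saline (single shot adductor canal group), or ropivacaine 0.2"%; no programmed rate for saline is given. No fill volume is stated for any arm.

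The Aim 2 endpoint takes three forms. Section 3.5 names "the amount of medication administered via the patient-controlled function on the adductor catheter". The hypothesis in section 7.2 is that "the intermittent bolus cohort will require fewer doses of patient-administered medication" than the continuous and placebo groups. Section 3 (the supplier's report) and section 3.7 (the data items) both describe a rate of on-demand use, recorded once, without saying per what. Section 3.7 lists the device serial number but no pump start, stop or empty time. By contrast, section 3.5 divides in-hospital morphine equivalents by hospital hours so that patients can be compared.

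**The concern.** A pump can answer a demand only while it still holds fluid. If the catheter comes out when the pump is empty, the time at risk for demand doses depends on the arm's programmed rate and on the patient's own demand. A raw count or volume then mixes need for extra analgesia with how long the pump lasted. Heavy users would also cut short their own count.

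Aim 2 is a named objective with its own directional hypothesis, and section 7.1 intends this study's data to supply the power calculation for a larger trial. An artefact of pump life could carry into that calculation.

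**Working it through.** **Inputs from the documents.** Programmed rate b = 6 mL/hr (continuous) and 8/2 = 4 mL/hr (bolus), section 3. Demand d between 0 and 6 mL/hr, reading section 3's demand dose as an hourly maximum. Stated end: 4 days = 96 h. Test: Wilcoxon rank sum, two-sided, 0.05/3 = 0.0167, with 28 per arm (section 7.2).

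**Assumptions.** Fill volume V is not given, so a range is used. Hourly demand is held constant over time.

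**Step 1: can an empty pump and day 4 coincide?** Time to empty is T = V/(b+d). The 4-day figure cannot be reproduced without V, so solve for V: emptying at 96 h needs V = 96(b+d).
- No demand: 96 × 6 = 576 mL against 96 × 4 = 384 mL.
- One common fill empties at 96 h in both arms only if 6+d(continuous) = 4+d(bolus), that is, only if every bolus patient demands exactly 2 mL/hr more than every continuous patient.
- Arm-specific fills of 576 and 384 mL match only if nobody presses. At d = 2 they empty at 576/8 = 72 h and 384/6 = 64 h.
- A fill that outlasts 96 h for everyone (96 × 12 = 1152 mL and 96 × 10 = 960 mL at maximum demand) is generally not empty at removal.

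Slack in what counts as day 4 does not rescue this. With a common 576 mL and no demand, the pumps empty at 96 h and 144 h; at maximum demand, at 48 h and 57.6 h.

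**Step 2: effect on the raw amount if emptying governs and fills are equal.** Demand volume is d × V/(b+d). At equal d the ratio of bolus to continuous is (6+d)/(4+d), whatever the fill:

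| d (mL/hr) | Ratio |
|---|---|
| 0.5 | 1.44 |
| 1 | 1.40 |
| 2 | 1.33 |
| 3 | 1.29 |

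Example with an assumed 500 mL and d = 1: 71.4 mL over 71.4 h against 100 mL over 100 h. Heavy use is also compressed within an arm. In the continuous arm, tripling d from 1 to 3 raises the recorded volume only from 71.4 to 166.7 mL, a factor of 2.33.

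**Step 3: effect if the pump stops at 96 h or when empty, whichever comes first.** At d = 1 the ratio is 1.40 for 400 mL, 1.34 for 500 mL and 1.12 for 600 mL. It reaches 1 once the fill is at least 96 × 7 = 672 mL.

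**Step 4: effect on the planned test.** Simulation with 28 per arm, 2000 runs, and identical hourly demand in both arms (assumed gamma, shape 2, mean 1 or 2 mL/hr, maximum 6). Rejection should be about 0.0167.

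| Analysis | Rejection rate |
|---|---|
| Raw amount, emptying governs, equal fills | 0.29 to 0.32 |
| Raw amount, 96 h cap, 400 mL | 0.30 to 0.31 |
| Raw amount, 96 h cap, 500 mL | 0.15 to 0.28 |
| Raw amount, 96 h cap, 600 mL | 0.03 to 0.10 |
| Raw amount, 96 h cap, 800 mL or more | about 0.015 to 0.020 |
| Demand per pump hour, all cases | about 0.012 to 0.021 |

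The last row is expected, because with constant demand the hourly rate is simply d. It does not test demand that changes over the postoperative days.

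**The case against.** The strongest reply is that a fixed end is at least as natural a reading. Section 5.9.4 itself names day 4, the Study Summary gives 4 days, and the wording about an empty pump sits in sections on packaging, storage and return rather than in the dosing description. On that reading, with an ample fill, every patient has the same window and the raw amount is comparable. This stands, and it makes the concern conditional. It does not remove the conflict, because no section says which event governs or what the fill is.

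Second, what is collected is called a rate in sections 3 and 3.7, so it may already be normalised. That is possible, but the denominator is undefined and the endpoint in section 3.5 is an amount.

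Third, this is a secondary endpoint in a study sized for feasibility, and with equal fills the bias works against the bolus hypothesis. True, but the direction is not assured. With fills of 576 and 384 mL and d = 2, the volumes are 2 × 72 = 144 mL (continuous) and 2 × 64 = 128 mL (bolus), the opposite direction.

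Three stronger readings are tempting and are not supported:
- A reader might infer from 576 − 384 = 192 mL that the continuous arm always has 32 six-mL demand doses less room. That holds at 96 h only for common fills of at least 576 mL. At 500 mL the gap is 116 mL, at 400 mL 16 mL, and at 384 mL zero. From 1152 mL it constrains nobody.
- A reader might infer that saline-arm demand is zero by design and should leave the Aim 2 test. But every group has a demand dose and the hypothesis counts doses, so blinded presses are meaningful in all three arms.
- A reader might infer that pain scores on days 3 and 4 are distorted. That is plausible if emptying governs, but nothing in the documents allows it to be sized.

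**Conclusion.** The concern holds in conditional form. The conflict between an empty pump and day 4 is a matter of arithmetic and stands whatever the fill volume. Its effect on Aim 2 depends on facts the documents leave out. If emptying governs and the two active arms have equal fills, equal hourly demand gives a raw amount 1.40 times larger in the bolus arm at 1 mL/hr and 1.33 times at 2 mL/hr, and the planned test would reject in roughly 30% of trials under the assumed demand distribution. If day 4 governs and the fill is ample (about 800 mL or more in these scenarios; 1152 and 960 mL guarantee it), there is no distortion.

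The bias for the saline arm cannot be computed because its programmed rate is not stated. The point concerns a secondary endpoint and should be settled before the supplier's data are requested and analysed.

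**What to change.** 1. Reconcile the Study Summary and section 5.9.4, with sections 5.7 and 5.9.2, so that one stated event ends the infusion in all arms. Which event is the sponsor's choice. State the fill volume and the saline arm's programmed rate.
2. Ask the supplier for pump start time and stop or empty time along with the usage report, and add them to section 3.7.
3. Define Aim 2 once, in sections 3.5 and 7.2, as demand doses delivered per hour of pump operation. Apply it in all three arms, keep the three planned pairwise comparisons, and count saline-arm presses as doses rather than as medication.
4. If the supplier can provide time-stamped presses, add a sensitivity analysis over a common early window in which pumps in all arms are still running.

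The cost is protocol wording and one or two extra data fields; step 4 needs more detailed data than the single usage rate now described. The limitation is that a rate removes differences in exposure length but not differences in which postoperative hours are sampled, so it can still mislead if demand falls over time. Step 4 addresses that, at the price of dropping later presses from that analysis.
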